8.2 Minimization of Risks

Potential risks associated with the use of the GORE® Hybrid Vascular Graft may be minimized by the following activities:

- Testing: The Sponsor has performed qualification testing on the device and device components and appropriate quality control measures have been implemented into production. Investigators will be selected who are knowledgeable and experienced in vascular graft implantation procedures.
- Training: Comprehensive Site Investigator and staff training will be conducted to share information regarding design and proper use of the GORE® Hybrid Vascular Graft.
- Training: The Site Investigator, Sub-Investigators, Study Coordinator(s) or designee at each Site will be trained to the protocol and Subject follow-up requirements.
- Screening: Protocol inclusion / exclusion criteria and follow-up schedule are designed to select appropriate Subjects and identify potential complications early. Subjects will be assessed post-procedure and subsequently on a regular basis at their follow-up visits.
- Monitoring: Data completed by the clinical Sites will be monitored to evaluate protocol compliance, accuracy, and Subject safety.
- Sharing: Data during the clinical study will be shared with the Site Investigators to aid understanding of the device and potential complications associated with its use.

9. Adverse Events

Adverse events (AEs) are defined as any untoward medical occurrences in a Subject whether device-related or not.

9.1 Anticipated Adverse Events

Anticipated adverse events are complications that are known to be associated with hemodialysis patients undergoing the creation of vascular graft access. See Section 8, Risk Assessment.

The Sponsor considers occurrences of thrombosis and stenosis to be efficacy outcomes and not adverse events. These occurrences should be reported on a Revision to Circuit CRF.

Should there be clinical sequelae associated with thrombosis and stenosis, these sequelae are considered adverse events and should be reported.

CONFIDENTIAL INFORMATION

[REDACTED] Protocol Template

Revision#: 1

Doc Type: GC

9.2 Adverse Event Relationship

Each reported AE will be assessed by the Investigator for its primary suspected relationship to the device, procedure, or disease.

Study Device-related (Hybrid or Control Graft)

The functioning or characteristics of the device caused or contributed to the AE.

Study Procedure-related (Index Procedure)

The index procedure (and not the device) caused or significantly contributed to the AE.

Disease-related (ESRD only)

The AE was a result of the underlying disease progression, for which the study procedure is being performed, and not the device or procedure.

Not-related

An AE which cannot be attributed to the device, procedure, or disease.

Unknown relationship

The relationship of the AE to the device, procedure, or disease cannot be determined.

9.3 Adverse Event Classification

The Investigator at each Investigative Site is ultimately responsible for reporting AEs to the Sponsor. The Investigator is required to complete the appropriate CRFs to report the occurrence of AEs.

Each AE will be assessed by the Investigator to determine if it is a serious adverse event (SAE).

A Serious Adverse Event (ISO 14155 definition) is an Adverse Event that

- led to death
- led to serious deterioration in the health of the Subject that either resulted in
 - a life threatening illness or injury, or
 - a permanent impairment of a body structure or body function, or
 - inpatient or prolonged hospitalization, or
 - medical or surgical intervention to prevent life threatening illness or injury or permanent impairment to a body structure or a body function
- led to fetal distress, fetal death, or a congenital abnormality or birth defect.

Emergency room visits and 23-hours observations are not considered hospitalizations.

CONFIDENTIAL INFORMATION

[REDACTED] Protocol Template

Revision#: 1

Doc Type: GC

9.4 Adverse Event Reporting and Coding

AEs will be reported on the appropriate case report form and documented in the Subject's permanent medical record.

The following information on each reported adverse event will be collected:

- Adverse Event Term
- Adverse Event Onset Date
- Relationship
- Severity
- Treatment
- Outcome
- Resolution Date

AEs will be coded using the Medical Dictionary for Regulatory Activities (MedDRA).

AE submission guidelines:

- AE reporting begins once the patient is enrolled in the study. All AEs should be reported from enrollment (study procedure) through study completion / discontinuation.
- Provide a diagnosis if possible. If unable to provide a diagnosis, report the symptoms as separate events. AEs should be reported using the full name without abbreviations or narratives.
- AEs with an outcome status of "Ongoing" should be assessed at each follow-up evaluation to determine if the event has resolved. AEs ongoing at study completion / discontinuation should be completed as "Ongoing" on the AE CRF.

9.5 Subject Death

When a Subject in the study expires, the primary cause of death will be identified as the AE. If any AEs have been reported as "Ongoing" up through the time of a Subject's death, these events would then become resolved with the date of death.

An effort by the Site should be made to collect additional information regarding the Subject's death. Documents include, but are not limited to: autopsy reports, death certificates, lab reports, and other applicable medical records.

A Study Completion / Discontinuation CRF will be completed for each Subject who expired during the course of the study.

CONFIDENTIAL INFORMATION

[REDACTED] Protocol Template

Revision#: 1

Doc Type: GC

10. Statistical Analysis

10.1. Study Hypothesis

[REDACTED]

The hypothesis is specified as follows:

[REDACTED]

[REDACTED]

10.2. Sample Size Assumptions

[REDACTED]

[REDACTED]

10.3. Sample Size Determination

[REDACTED]

10.4. Randomization Scheme

The randomization will be organized using [REDACTED]

[REDACTED] Any irregularity in the randomization process will be documented and reported to the Sponsor.

10.5. Blinding Scheme

The Subjects, as well as treating physicians, will be aware of the type of implanted graft. However, the core laboratory responsible for analyzing the blood samples will be blinded to the actual type of graft.

10.6. Data Analysis

10.6.1. Timing of Analyses

[REDACTED]

CONFIDENTIAL INFORMATION

[REDACTED] Protocol Template

Revision#: 1

Doc Type: GC

10.6.2. Analysis Populations

10.6.2.1. Intent-To-Treat (ITT)

The intent-to-treat population is defined as all enrolled subjects analyzed by the assigned treatment arm at the time of randomization.

10.6.2.2. As Treated

The “as treated” population is defined as all subjects analyzed by type of the actual implanted device.

10.6.3. Pooling of Data

Data will be pooled from all Sites participating in the trial. To help ensure homogeneity of data across Sites, the protocol will be administered and monitored in a uniform manner at all Sites.

10.6.4. Statistical Analysis of Primary Endpoint(s)

CONFIDENTIAL INFORMATION

[REDACTED] Protocol Template

Revision#: 1

Doc Type: GC

11. Ethical and Regulatory Considerations

11.1. Statement of Compliance

The study will be conducted in compliance with this protocol, International Conference on Harmonization Good Clinical Practice E6 (ICH-GCP), and applicable regulatory requirements.

The following are applicable to this study:

21 CFR Part 11	Electronic Records; Electronic Signatures
21 CFR Part 50	Protection of Human Subjects
21 CFR Part 56	Institutional Review Boards
ICH-GCP E6	International Conference on Harmonisation Regulations Guideline For Good Clinical Practice

11.2. Compliance Responsibilities

The Sponsor will conduct the clinical study in accordance with all applicable regulations and laws. The Sponsor will be responsible for documenting that Investigators have the necessary skills, training, and information to properly conduct the clinical study. The Sponsor will ensure proper monitoring of the clinical study and ensure the Site has obtained IRB approval prior to enrollment. The Sponsor will provide information to the Investigators and the reviewing IRB concerning the progress of and any new material information about the clinical study.

The Investigator will conduct the clinical study in accordance with all applicable regulations and laws, any relevant agreements, the study protocol, and all approval conditions of the reviewing IRB. The Investigator will ensure IRB approval is obtained prior to enrollment, maintained throughout the course of the study, and all IRB reporting requirements are met. The Investigator is responsible for protecting the rights, safety, and welfare of Subjects under the Investigator's care and for the control of devices under investigation. The Investigator is also responsible for ensuring informed consent is properly obtained.

11.3. Informed Consent

The Investigator shall ensure all potential Subjects for this study are provided with a consent form describing this study and sufficient information to make an informed decision about their participation.

CONFIDENTIAL INFORMATION

Protocol Template

Revision#: 1

Doc Type: GC

Page 27 of 29

The formal consent of a Subject, using the IRB-approved consent form, must be obtained by the Investigator before that Subject undergoes any study-related procedure. The consent form will be signed and personally dated by the Subject or legally authorized representative, and the person who conducted the informed consent discussion. The original signed informed consent form will be retained in the Subject records. A copy of the signed informed consent document will be given to the Subject for his or her records. Any significant, new information which emerges while the study is in progress that may influence a Subject's willingness to continue to take part in the study will be provided to the Subject.

The Investigator shall ensure documentation of the acquisition of informed consent is recorded in each Subject's records in accordance with applicable regulations.

11.4. Independent Ethical Review

The Investigator shall not enroll any Subjects prior to obtaining approval for the study from a properly constituted independent IRB.

The Investigator will submit the protocol, informed consent forms, other information to be provided to Subjects such as survey instruments or questionnaires, and any proposed advertising / recruitment materials to the IRB for written approval.

11.5. Conflict of Interest

All Investigators will follow their Institution's conflict of interest policies.

11.6. Confidentiality

All Subject records will be kept confidential to the extent provided by applicable laws and regulations. The study monitors and other authorized representatives of the Sponsor may inspect all documents and records required to be maintained by the Investigator, including but not limited to medical records.

Such records may also be reviewed by the Site's IRB and other regulatory bodies.

The Investigator will inform the Subjects their records will be reviewed.

CONFIDENTIAL INFORMATION

[REDACTED] Protocol Template

Revision#: 1

Doc Type: GC

12. References

A series of 10 horizontal black bars of varying lengths, decreasing from left to right, representing a data distribution.

CONFIDENTIAL INFORMATION

Protocol Template

Revision#: 1

Doc Type: GC

Statistical Analysis Plan

Study Acronym / Protocol #: HVG 13-01

CONFIDENTIAL INFORMATION

[REDACTED] Statistical Analysis Plan Template
Revision#: 1
Doc Type: GC

Table of Contents

| | |
|---|----|
| 1. Introduction | 4 |
| 2. Study Design Overview | 4 |
| 2.1. Objectives | 4 |
| 2.2. Design Summary | 5 |
| 2.3. Study Endpoints | 5 |
| [REDACTED] | 5 |
| [REDACTED] | 6 |
| [REDACTED] | 7 |
| 2.4. Potential Risks | 7 |
| 2.5. Randomization Scheme | 7 |
| 2.6. Blinding Scheme | 8 |
| 2.7. Statistical Hypotheses | 8 |
| 2.8. Sample Size Assumptions | 8 |
| 2.9. Sample Size Calculations | 8 |
| 3. Study Treatment Arms | 8 |
| 3.1. Test Arm | 8 |
| 3.2. Control Arm | 8 |
| 4. Study Data Collection | 9 |
| 4.1. Enrollment | 9 |
| 4.2. Follow-Up Intervals | 9 |
| 5. Statistical Analyses | 9 |
| 5.1. Timing of Analysis | 9 |
| 5.2. Analysis Population | 9 |
| 5.3. Primary Endpoints | 10 |
| 5.4. Additional Assessments | 10 |
| 5.5. Comparison of baseline characteristics | 10 |
| 5.6. Adverse Events | 10 |
| 5.7. Pooling of Data | 11 |

CONFIDENTIAL INFORMATION

| | |
|---|----|
| 5.8. Sub-group Analysis:..... | 12 |
| 6. Analysis Specifications | 12 |
| 6.1. SAS Analysis Dataset Specifications | 12 |
| 6.2. Statistical Output Specifications..... | 12 |
| 6.3. Verification Level for Statistical Output..... | 12 |
| 7. Data Sets, Tables, Figures, and Listings..... | 12 |
| 7.1. Analysis Tables..... | 12 |
| 7.2. Analysis Listings | 13 |
| 7.3. Analysis Figures | 14 |
| 7.4. Analysis Data Sets..... | 14 |
| 8. References | 14 |

CONFIDENTIAL INFORMATION

1. Introduction

This Statistical Analysis Plan (SAP) describes the statistical analyses planned to address the objectives of HVG 13-01. This SAP summarizes the analyses that will be performed to characterize the safety and efficacy of the GORE® Hybrid Vascular Graft as compared to non-heparin bonded synthetic vascular grafts in term of the prevalence and persistence of anti-platelet factor 4/heparin antibodies (anti-PF4/H antibodies). This SAP exhibits tables, figures, and listings that will be prepared as part of the final study report.

2. Study Design Overview

This is a prospective, multicenter, randomized clinical evaluation to characterize the GORE® Hybrid Vascular Graft by comparing non-heparin bonded synthetic vascular grafts in terms of the prevalence and persistence of anti-PF4/H antibodies up to Day 90.

[REDACTED]

Subjects may continue into the extended portion of this clinical study (post Day 90) provided that they have re-consented and the vascular graft has not been abandoned. Subjects will be evaluated post Day 90 and return for follow-up visits at Month 6 and Month 12.

[REDACTED]

Follow up Schedule

- **Day 7 (± 2 days)** - Collection of blood and serum samples, adverse events, and revisions to the circuit
- **Day 14 (± 2 days)** – Collection of blood and serum samples, adverse events, and revisions to the circuit
- **Day 30 (± 7 days)** – Collection of blood and serum samples, [REDACTED]
[REDACTED], adverse events, and revisions to the circuit
- **Day 90 (± 14 days)** – Collection of blood and serum samples, [REDACTED]
[REDACTED] adverse events, and revisions to the circuit
- **Month 6 (± 14 days)** - [REDACTED], adverse events, and revisions to the circuit
- **Month 12 (± 14 days)** - [REDACTED], adverse events, and revisions to the circuit

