3.1. Study Design Schema

3.2. Description of Study Design

This is a prospective, multicenter, randomized clinical evaluation to characterize the GORE® Hybrid Vascular Graft by comparing non-heparin bonded synthetic vascular grafts in terms of the prevalence and persistence of anti-PF4/H antibodies up to Day 90.

[REDACTED]

CONFIDENTIAL INFORMATION

Protocol Template

Revision#: 1

Doc Type: GC

Subjects may continue into the extended portion of this clinical study (post Day 90) provided the vascular graft has not been abandoned. Subjects will return for follow-up visits at Months 6 and 12. The control device is a non-heparin bonded synthetic vascular graft that is indicated for use for dialysis access. The control graft may be composed of any synthetic material including, but not limited to: [REDACTED]

[REDACTED] The brand of the control device is at the discretion of the Investigator. [REDACTED]

A maximum of 25 Clinical Investigative Sites (referred to as "Sites" in the remainder of this document) in the United States will participate in this study. [REDACTED]

Follow-up Schedule

- **Day 7 (± 2 days)** - Collection of blood and serum samples, adverse events, and revisions to the circuit
- **Day 14 (± 2 days)** – Collection of blood and serum samples, adverse events, and revisions to the circuit
- **Day 30 (± 7 days)** – Collection of blood and serum samples, [REDACTED], adverse events, and revisions to the circuit
- **Day 90 (± 14 days)** – Collection of blood and serum samples, [REDACTED], adverse events, and revisions to the circuit
- **Month 6 (± 14 days)** - [REDACTED], adverse events, and revisions to the circuit
- **Month 12 (± 14 days)** - [REDACTED], adverse events, and revisions to the circuit

Patients may be enrolled into the clinical study provided all inclusion and no exclusion criteria are met as specified in Section 4. Subjects will be evaluated through surgical discharge and return for follow-up visits at Days 7, 14, 30, 90, Months 6 and 12.

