5.3 Informed Consent Process

All patients must provide informed consent prior to any study-related procedures being performed. The case history (*i.e.*, source documents / Subject chart) for each Subject shall document such informed consent was obtained. The Institutional Review Board (IRB) approved consent form (ICF) will be signed and personally dated by the Subject or his / her legally authorized representative, and the Investigator / designee who conducted the informed consent discussion.

Subjects enrolled under the original protocol (3-DEC-2013) should not be re-consented under Amendment 2 [REDACTED] if:

- the vascular graft has been abandoned prior to the Day 90 follow-up visit
- the vascular graft has been explanted

CONFIDENTIAL INFORMATION

[REDACTED] Protocol Template

Revision#: 1

Doc Type: GC

[REDACTED]

[REDACTED]

[REDACTED]

The original signed ICF(s) will be retained in the Subject records. A copy of the signed informed consent document will be given to the Subject for their records.

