6.3. Verification Level for Statistical Output

- The Analysis Datasets, Tables and Listings will be validated using the following levels as defined in the [REDACTED].
- All Analysis Datasets – Level I
- All Tables – Level I
- All Listings – Level II

7. Data Sets, Tables, Figures, and Listings

At a minimum, the following set of Tables, Figures, and Listings will be produced for both arms separately and combined together. Unless specified, the population for all tables is the “Intent-to-Treat”.

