7.1. Analysis Tables

- Subject Demographics [REDACTED]

CONFIDENTIAL INFORMATION

[REDACTED] Statistical Analysis Plan Template

Revision#: 1

Doc Type: GC

Page 12 of 14

- Subject Physical Exam [REDACTED]
- Subject Lab Results [REDACTED]
- Subject Medical History [REDACTED]
[REDACTED]
- Anticoagulant and/or antiplatelet therapies within the past 6 months [REDACTED]
[REDACTED]
- Summary of Enrollment by Site [REDACTED]
- Summary of Vascular Access History [REDACTED]
[REDACTED]
- Summary of Device Use [REDACTED]
[REDACTED]
- Summary of Procedural Assessments [REDACTED]
[REDACTED]
- Subject Status/Reason for Withdrawal [REDACTED]
[REDACTED]
[REDACTED]
- Summary of positive poly-specific enzyme immunoassay (EIA) [REDACTED]
- Summary of Anti-PF4/H antibody seroconversion
- Summary of Anti-PF4/H antibody seroreversion
- Summary of positive IgG-specific EIA at Day 7 and / or Day 14
- Summary of positive full serotonin release assay (SRA) panel
- Summary of platelet count at Pre-procedure, Day 7, 14, 30, and 90
[REDACTED]
[REDACTED]
[REDACTED]
[REDACTED]
- Summary of All Adverse Events by MedDRA SOC, PT

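### Adverse event follow-up after Day 90 depends on graft survival, and the visible AE summary has no common time window or person-time denominator

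*SAP*

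**What the plan says.** Two conditions govern follow-up after Day 90. Protocol 3.2 gives one: "Subjects may continue into the extended portion of this clinical study (post Day 90) provided the vascular graft has not been abandoned". SAP section 2 adds a second: "provided that they have re-consented and the vascular graft has not been abandoned". Protocol 5.3 tells sites not to re-consent subjects enrolled under the original protocol if "the vascular graft has been abandoned prior to the Day 90 follow-up visit" or if "the vascular graft has been explanted".

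AE collection has no fixed end. Protocol 9.4 states: "All AEs should be reported from enrollment (study procedure) through study completion / discontinuation". In the SAP follow-up schedule, the Month 6 and Month 12 visits both include "adverse events, and revisions to the circuit".

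On reporting, SAP section 7 has outputs produced for each arm and combined, and adds: "Unless specified, the population for all tables is the “Intent-to-Treat". The AE entry visible in SAP 7.1 is "Summary of All Adverse Events by MedDRA SOC, PT". The visible text of SAP 5.6 covers definitions, relationship and seriousness. It gives no cut-off day, no person-time rate and no time-to-event method. SAP 5.6.1 treats thrombosis and stenosis as efficacy outcomes rather than AEs, but counts their clinical sequelae as AEs.

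**The concern.** Graft abandonment happens after randomisation and may differ by arm. The Protocol's introduction attributes about 80% of graft failures to thrombosis and presents bonded heparin as a possible way to reduce it, so different graft survival is a possible effect of the test device. A subject who loses the graft early stays in the denominator but cannot contribute an event after follow-up ends, and the thrombosis behind the loss is not itself counted.

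A plain by-arm count or percentage over the whole study then compares groups observed for different lengths of time. It could flatter whichever arm loses more grafts. If the heparin surface preserves grafts, it could instead make the test device look worse because its subjects are watched longer. AEs recorded at Months 6 and 12 come only from subjects who entered the extension, so on their own they are not a randomised comparison.

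**Working it through.** The documents state no figure to reproduce: the sample size section is redacted, and no AE or abandonment rate is visible. The check is person-time arithmetic under assumed rates.

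**Inputs.**
- From the documents: follow-up of about 90 days without the extension, and about 365 days with it (12 months taken as 365 days).
- Assumed: q, the share of an arm that does not enter the extension because of early graft loss; λ, AEs per patient-year, constant and equal in both arms; x, extra AEs that come with a graft loss.
- Also assumed: a subject with early loss is followed to Day 90. The visible text does not say exactly when such a subject leaves.

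**Step 1. Observation time.** A subject who stops at Day 90 is watched for 90/365 = 24.7% of the full period, 275 days fewer. With the ±14-day visit window the share is 76/365 = 20.8% to 104/365 = 28.5%.

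**Step 2. Mean follow-up by arm.** As a share of the full period this is 1 − q × (1 − 90/365) = 1 − 0.753q. With x = 0 and equal λ, crude AE counts per subject are in the same ratio.

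| Early loss, lower vs higher arm | Mean follow-up share | Ratio, higher-loss / lower-loss arm |
|---|---|---|
| 5% vs 10% | 0.962 vs 0.925 | 0.961 |
| 5% vs 15% | 0.962 vs 0.887 | 0.922 |
| 10% vs 20% | 0.925 vs 0.849 | 0.919 |
| 10% vs 30% | 0.925 vs 0.774 | 0.837 |

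The crude count is therefore about 4% to 16% lower in the higher-loss arm, with no true difference in risk. With equal loss the ratio is 1.

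**Step 3. Percentage with any AE.** P = (1 − q)(1 − e^(−λ)) + q(1 − e^(−λ × 90/365)). At 10% vs 20% early loss (differences taken before rounding):
- λ = 0.5: 36.6% vs 33.8%, a gap of 2.8 points
- λ = 1: 59.1% vs 54.9%, 4.1 points
- λ = 2: 81.7% vs 77.0%, 4.8 points

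**Step 4. Can the direction change?** Expected AEs per subject are (1 − q)λ + q(λ × 90/365 + x). The arms tie when x = λ × 275/365, which is 0.38, 0.75 or 1.51 extra AEs per loss at λ = 0.5, 1 or 2. At 10% vs 20%, λ = 1 and x = 1:
- lower-loss arm: 0.9 + 0.1 × 1.247 = 1.025
- higher-loss arm: 0.8 + 0.2 × 1.247 = 1.049
- ratio: 1.024, so the higher-loss arm now shows slightly more AEs.

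**Step 5. With the change.** With equal λ and x = 0, either a Day 90 cut or a person-time denominator gives a ratio of 1.00.

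**The case against.** The strongest objection is that this concerns a descriptive secondary table. The objective is antibody prevalence and persistence, which Protocol section 2 limits to Day 90, and the primary endpoint uses Days 7 and 14. A reader might take the words on safety and efficacy in SAP section 1 as a promise of a general safety comparison, but that sentence goes on to qualify them in terms of the antibodies. No visible text plans a formal between-arm AE test. This stands and limits the importance of the point.

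Second, a reader might infer that the arm with more graft losses will show fewer AEs. The documents do not support that. They give no loss rates by arm, and sequelae of thrombosis and stenosis count as AEs, so the deficit can cancel or reverse. If AEs cluster around the index procedure, less is missed after Day 90 than a constant rate implies. All of this stands.

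Third, the intent-to-treat population is not the cause. An as-treated table would have the same unequal follow-up.

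Fourth, redaction. The timing of analyses, the additional assessments, and several table and listing lines cannot be read, and SAP 6.2 leaves layout to output specifications. A Day 90 cut could already exist, so the absence holds for the visible text only.

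Fifth, part of the remedy is planned: a by-arm table of subject status and withdrawal reasons, and listings of AEs and of completion or discontinuation. These would largely show differential exit, but they would not correct the AE summary.

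Finally, it is tempting to suppose that Months 6 and 12 summaries in general will be mixed with the earlier randomised data. Apart from the AE summary, no visible table is tied to those visits.

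**Conclusion.** The point holds in a conditional form. Follow-up after Day 90 depends on a post-randomisation outcome, and on re-consent under the SAP. The visible AE summary has nothing to put the arms on a common footing. If early graft loss differs by arm, crude AE comparisons are confounded with graft survival.

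Other things equal, the lean is toward fewer AEs in the arm with more loss, of the order of 4% to 16% in counts over the assumed scenarios. Those scenarios rest on a constant AE rate equal in both arms, follow-up of 90 versus 365 days, and no extra AEs with graft loss. Relaxing the last assumption can remove or reverse the effect, so neither its sign nor its size can be predicted from the documents. The primary endpoint is untouched. This is a reporting weakness in the AE comparison that is cheap to repair.

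**What to change.** Unless a redacted section already does so, amend SAP 5.6 and 7.1 as follows.

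- Make the main by-arm AE summary the period from the index procedure through Day 90. Give person-time by arm for this window too. It is only approximately equal, because Protocol 5.5 discontinues randomised subjects who cannot complete the procedure and Protocol 5.11 lists explant among the reasons for ending participation.
- Report AEs through Month 12 as rates per patient-year from the index procedure, with observation time by arm. Read these beside the Day 90 figures, since a single rate over unequal follow-up is itself distorted if AEs are concentrated early.
- Label Month 6 and Month 12 summaries as describing subjects who entered the extension. State how many randomised subjects per arm did not enter and why (abandonment, explant, no re-consent, other). Do not present them as a randomised comparison. Recording the reason matters because Protocol 5.10 classes anyone without a Month 12 visit as lost to follow-up, with no visible exception for subjects not eligible to continue.

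The cost is SAP wording, one extra table split and slightly more programming. AE onset dates and completion or discontinuation data are already collected, and no visits are added.
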